As part of the Smart Hospital Project, this Study and potential future research studies to improve the quality, accuracy and efficiency of monitoring neonates admitted in the NICU, the participants' information may be shared with academic or commercial third parties and used by the research team in other related research studies. Any use of the RI-MUHC and participating site's data in future research studies will be approved by competent research ethics boards and no data that could identify the participant will be shared. Participants at all participating sites will be asked to consent to the sharing of their data collected during this study as well as for use in future research in the field of neonatal care and monitoring. The participants' data will be kept confidential to the extent required by applicable laws. The research agreements with the participating sites will include all the terms and conditions required for the use and sharing of the data from participating sites.

4 Statistical Analysis and Rationale

Sample size: The proposed sample size is 100 newborns/site (n=600) to be recruited over 2 years from start of the Study at each site.

The expected mean and standard deviation are required for estimating the mean effects which is used to determine the absolute precision. In our first study with wireless sensors (see preliminary data) or *phase 1a*, 100 patient recordings (25 infants x 4 days) were expected but only 96 were obtained, resulting in a 4% drop-out rate. Further, the average coverage across wired HR signals was $98.7 \pm 2.2\%$, while that of wireless signals was $85.3 \pm 14.3\%$. Assuming a two-sided significance of 0.05, a study power of 0.9, and accounting for the drop-out rate of 0.04 in all calculations, we can expect an effect size of 2.7% in HR coverage, with the selected sample size of 600 infants. In the case of SpO₂ monitoring, the average coverage was $93.9 \pm 6.3\%$ in the wired system and $66.5 \pm 20.8\%$ in the wireless. In our proposed study, we

can thus expect a difference of 3.46% in SpO₂ coverage. For the statistical measures used to assess the agreement between the wired and wireless vital signals, the average findings from *phase 1a* are reported in the Table. Using the same parameters listed previously, the margin of error expected for each statistical measure in the proposed study can be found.

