Statistical measure		Correlation coefficient, C	Proportionality constant, k	Variance accounted for (VAF)	Mean difference (bias), d
Average result in phase 1a	Heart rate (HR)	0.96 ± 0.03	1.00 ± 0.00	91.5 ± 6.5%	0.04 ± 0.32 bpm
	Oxygen saturation (SpO ₂)	0.53 ± 0.23	1.01 ± 0.01	18.9 ± 20.8%	1.43 ± 1.4%
Expected margin of error	Heart rate (HR)	0.01	0.00	1.24%	0.06 bpm
	Oxygen saturation (SpO ₂)	0.04	0.00	3.97%	0.26%

Statistical analytical approach: Descriptive analyses will first be applied to the demographic data. Accuracy analysis of the wireless system to capture the vital signs will be done by using a statistical measure of the strength of a linear relationship between the two systems (correlation coefficient), a measurement of the steepness of this correlation (slope), the ratio of explained and target variance (variance accounted for), and a Bland-Altman plot analysis to evaluate *bias* between the mean differences and estimate an agreement interval.

Each participating site has the facilities and capacity to provide the estimated number of infants to establish feasibility, safety, and accuracy of the device. The wireless device sensors and system being used in the study is approved by Health Canada for research on neonates. Each site will obtain approval from their local and country specific health authorities, as required.

5 Ethical, Legal and Regulatory Considerations

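### The Aim 3 slope has no defined estimator, and the tabulated constant k behaves like a through-origin ratio that nearly repeats the bias and misses compression offset by an intercept

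*Combined protocol and SAP*

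**What the plan says.** Section 2.2 lists four accuracy outcomes under Aim 3: correlation coefficient, slope, variance accounted for (VAF) and bias. The analytical approach in section 4 describes the second as "a measurement of the steepness of this correlation (slope" and the third as "the ratio of explained and target variance (variance accounted for". It adds "a Bland-Altman plot analysis to evaluate" bias and estimate an interval of agreement.

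The table in section 4, which gives phase 1a results and expected margins of error, has no slope column. Its second column is headed "Proportionality constant", with symbol k:

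- HR: C 0.96 ± 0.03, k 1.00 ± 0.00, VAF 91.5 ± 6.5%, bias 0.04 ± 0.32 bpm.
- SpO2: C 0.53 ± 0.23, k 1.01 ± 0.01, VAF 18.9 ± 20.8%, bias 1.43 ± 1.4%.
- Expected margin for k: 0.00 for both signals.

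The documents do not say how k or the slope is estimated, whether an intercept is fitted, or how the two relate. They set no criterion for the slope and state no analysis of how the differences change with the level of the signal.

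**The concern.** A slope is normally reported to show whether one device stretches or compresses changes relative to the other. In the table, k is about 1 both for a signal that tracks well (HR) and for one that tracks poorly (SpO2). If the planned slope is this k, it may stay near 1 even when the wireless sensor flattens a fall in SpO2 or HR. Flattening of that kind could contribute to the missed events that Aim 2c counts. If the planned slope is instead fitted with an intercept, the table's pilot values and its margin of 0.00 describe a different quantity, and no precision has been worked out for the outcome.

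**Working it through.** **1. The tabulated margins reproduce.** Inputs from section 4: "The proposed sample size is 100 newborns/site (n=600"; "Assuming a two-sided significance of 0.05, a study power of 0.9"; and "accounting for the drop-out rate of 0.04 in all calculations", so 600 × 0.96 = 576. The formula that fits is SD × (1.960 + 1.282) × √(2/576) = SD × 0.191.

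- VAF: HR 6.5 × 0.191 = 1.24; SpO2 20.8 × 0.191 = 3.97. Both match.
- Bias: HR 0.32 × 0.191 = 0.06, as stated. SpO2 1.4 × 0.191 = 0.267 against 0.26 stated (0.258 if the unrounded SD is 1.35).
- C: HR 0.0057 and SpO2 0.044, shown as 0.01 and 0.04.
- k: SpO2 0.01 × 0.191 = 0.002; HR 0.001 at most. Both round to 0.00.

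So the 0.00 is simply the small SD of k, rounded.

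**2. Can k be a least-squares slope with intercept?** That slope equals C × (SD of wireless / SD of wired).

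- With C = 0.53 and SD ratios of 0.8 to 1.25, it is 0.42 to 0.66. A value of 1.01 needs a ratio of 1.01/0.53 = 1.91.
- The ratio would also have to offset C almost exactly in each recording, for the slope to vary by only 0.01 while C varies by 0.23.
- With a fitted intercept, VAF = C². Mean VAF is then at least 0.53² = 28.1%, or 0.53² + 0.23² = 33.4% using the stated SD of C. The table says 18.9%. This check needs no assumed signal mean or SD, only that VAF and C come from the same fit and recordings.

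**3. Does a through-origin constant fit?** Take x as wired and y as wireless. Then k = Σxy/Σx² ≈ 1 + bias/mean. Signal means are not in the documents.

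- SpO2, assumed mean 90 to 98: k = 1.015 to 1.016, SD 0.014 to 0.016. Table: 1.01 ± 0.01.
- HR, assumed mean 120 to 160: k = 1.000, SD 0.002 to 0.003. Table: 1.00 ± 0.00.

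Agreement is to within about 0.01.

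**4. What such a k responds to.** Let b be the slope with intercept. Then k = (mean_x × mean_y + b × SD_x²)/(mean_x² + SD_x²). This is a weighted average of the ratio of means and b, in which b has weight SD_x²/(mean_x² + SD_x²). With assumed means and SDs:

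| Signal | Mean, SD | Weight on b | k at b = 0.5, no mean bias |
|---|---|---|---|
| SpO2 | 95, 3 | 9/9034 = 0.1% | 9029.5/9034 = 0.9995 |
| HR | 140, 15 | 225/19825 = 1.1% | 0.994 |
| Skin temperature | 36.5, 0.4 | 0.16/1332.41 = 0.01% | 0.9999 |
| RR | 50, 12 | 144/2644 = 5.4% | 0.97 |

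In the SpO2 example, the wireless reading when the wired monitor shows 80 is 95 + 0.5 × (80 − 95) = 87.5. That is above both SpO2 event limits in the documents (80% in Aim 2c, 85% in section 3.3.4), while k is 0.9995 and bias is 0.

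**5. What k does detect.** A pure scale error y = 1.10x gives k = 1.10. A constant HR offset of +10 bpm with true slope 1 gives 1 + 10 × 140/19825 = 1.07, which is also what a pure 7% scale error gives. So k moves with either error but cannot tell them apart.

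**6. Would the alternatives see the compression?** For true slope 0.5 and no mean bias, Deming regression recovers 0.50 if the error variances are equal, as assumed in the fit. Without noise, the differences change by −0.5/0.75 = −0.67 per unit of the mean. With noise the fall is nearer 0.6.

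**The case against.** The best defence is that slope is one descriptive measure among four. C and VAF sit beside it, a Bland-Altman plot would show a trend of −0.67 to the eye, Aim 2c counts missed events directly, and no success criterion depends on slope. The estimator is also inferred: the phase 1a methods are in cited reports that are not part of these documents, and k appears only in the table. All of this limits the harm. It does not remove the gap, because the stated Bland-Altman outputs are bias and an agreement interval, and compression balanced about the mean leaves bias at zero. The plan needs clarifying whichever quantity is meant.

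A reader might infer four stronger things that the documents do not support:

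- **That k cannot show proportional error.** It can: a pure multiplicative error moves it one for one. What it misses is a slope error offset by an intercept. Nor does it stay at 1 when bias is large, and for RR it is less insensitive (about 0.945 even at true slope 0).
- **That a margin of 0.00 proves k redundant.** The margin reflects only a small SD. The near-redundancy comes from k − 1 ≈ bias/mean.
- **That the low SpO2 correlation is itself proportional error.** With equal SDs, C = 0.53 is scatter: Deming (error-variance ratio 1) gives 1.00, and the slope of differences on mean is 0.
- **That a properly fitted SpO2 slope will look worse.** At C = 0.53, Deming gives 0.66, 1.00 or 1.43 for SD ratios of 0.8, 1 or 1.21. The documents do not give the ratio. Backing it out of the averaged k, C and VAF suggests about 1.21, which would be expansion, not compression.

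**Conclusion.** The point holds in a limited form. The slope outcome has no defined estimator, and the only figures given for it rule out a least-squares slope with intercept (SpO2 VAF of at least 28.1% implied, 18.9% stated) while fitting a through-origin constant. If that constant is the planned outcome, then at the small biases seen in phase 1a it adds almost nothing to bias for HR and SpO2, and the same would hold for skin temperature at a similarly small relative bias. It can read 0.9995 for a SpO2 sensor that halves every change.

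The VAF argument rests on the table alone. The size of the insensitivity rests on assumed means and SDs, though the weight on the true slope stays at or below about 1% for SpO2, HR and temperature at the values in the working. The 87.5 against 80 example is an extrapolation, since 80 lies 5 assumed SDs below the mean. Nothing here shows that the wireless sensor does compress readings; the point is that the stated outputs would not reliably reveal it.

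**What to change.** In section 4:

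1. State that the Aim 3 slope is estimated with an intercept.
2. For each infant and signal, report slope and intercept from an errors-in-variables method such as Deming regression. State the assumed error-variance ratio and vary it in a sensitivity analysis, because the documents give no value. Then summarise across infants.
3. Add a regression of the wireless-minus-wired differences on their mean, per infant, summarised the same way.
4. Define k explicitly, keep it only as a descriptive link to phase 1a, and note that the tabulated 0.00 margin belongs to k and not to the new slope.

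The cost is SAP wording and slightly more analysis of data already being collected. The new slope will be less precise than 0.00. As a rough guide, a least-squares slope with a constant SD ratio of 1 would vary across recordings as C does, and the plan's own formula then gives 0.23 × 0.191 = 0.044 for SpO2. The Deming margin will differ and should be worked out from the phase 1a recordings.

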Ongoing work includes the analysis of RR, SpO₂ and T_{skin} signals to evaluate the overall feasibility, reliability, and accuracy of ANNE® One sensors.

[figure not shown]

Figure 3. Cumulative histograms of HR recorded with a wired (blue) and a wireless system (red) for a typical subject

Additionally, we developed methods to synchronize and align all signals acquired from the wired and wireless monitors to allow sample-to-sample comparison.³³ (**Figure 4**).

[figure not shown]

Figure 4. The sample signals following pre-processing, where: (A) the short gap was filled, (B) aligned features share a common time due to resampling, (C) the initial delay was removed, and (D) the signals remain aligned 6 hours later due to drift correction.

More recently, the feasibility of this wireless system was evaluated by correlating periods of missing data in HR with automatically generated alert signals and manually recorded annotations. (**Figure 5**). Gaps in the wireless HR signals were most often linked to Bluetooth disconnections and KMC. Current work is examining the roles of: (1) movement artifact, (2) signal to-noise ratio, as a means to understand problems and improve the feasibility of using a wireless system in the NICU. ³⁴

[figure not shown]

Figure 5. Group results from HR gap classification pertaining to: (A) the correlation of gaps in the wireless system with alert flags, and (B) the correlation of gaps in both the wireless and wired systems with the seven-most prominent comment codes. HR sample coverage = 86%.

Based on these results and on interviews conducted with parents and NICU nurses, Sibel made important modifications to the ANNE One® chest sensor, including its size, shape (configuration), position of the antenna, and type of skin adhesive. The new sensor called ANNE Arc® is now available, has been approved by Health Canada for research (ITA), and will be used in this Study along with the RAD7 Limb Sensor (**Figure 6, Figure 7**). Moreover, a large international survey on the use of wired and wireless technology in the NICU was circulated to HCPs all over the world. Almost 1000 HCPs have replied, and analysis is underway. Finally, in collaboration with researchers at Northwestern University, a wireless acoustic device for

monitoring airflow, breathing efforts and bowel sounds was developed and tested. Results were presented at the PAS meeting in May 2023, and the manuscript was accepted for publication in *Nature Medicine*.³⁵

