2.2 Aims

Healthcare technology assessment is the multidisciplinary evaluation of medical technologies with regard to **feasibility, safety, efficacy**, indications for use, cost, and cost-effectiveness. A complete assessment should explore the scientific, ethical, economic, and social reasons for adopting a technology and it may influence the quality of service and distribution of resources.

In this multicenter study, we aim to assess the first 3 important criteria.

Aim 1 – To determine the **feasibility** of using a wireless system immediately after delivery and for the first 2h of age, while in the obstetrical center under unsupervised parents' care. The following outcomes will be measured for both wired and wireless systems:

- a. Percentage of time for which HR, RR, SpO₂ and T_{skin} data are displayed.
- b. Occurrence of gaps in signal detection/recordings (% and length).
- c. Causes of the gaps in signal detection/recordings.
- d. Descriptive analysis of user surveys and their satisfaction with the wireless system.

Aim 2 - To investigate the **safety** of using this wireless system immediately after delivery and for the first 2h of age. The following outcomes will be measured for both wired and wireless systems:

- a. Skin score to be determined by a blinded dermatologist using de-identified pictures of the skin after removal of the sensors of each system.
- b. Pain scale to assess any discomfort or pain during the removal of the sensors.
- c. Clinically significant events detected by the wired system (HR < 100 bpm or SpO₂ < 80%) but missed by the wireless system.

Aim 3 – To assess the **accuracy** of this wireless system in measuring HR, RR, SpO₂ and T_{skin} signals compared with the “standard of care” wired system. The following outcomes will be computed:

- a. Correlation coefficient
- b. Slope
- c. Variance accounted for
- d. Bias

Further subgroup analyses will be conducted to assess for systematic differences in feasibility, safety, and accuracy of the wireless system between the following:

- High vs. Low and Middle income countries
- Female vs. Male subjects
- Term vs. Preterm (born < 37 weeks gestational age) infants
- C-section vs. Vaginal delivery

- Skin pigmentation

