3.3.4 Data Collection

The Study research team at each site will collect standard demographic and clinical information from mothers and newborns as described in the Data Collection Form (see Appendix 1) during the 2hrs of vital sign recording (see Figure 11 below). With a stopwatch, a designated trained research team member(s) will time the recording as the period (sec.) that elapses from the application of the leads until the first display of data on the monitors, for all the sensors of both systems. Data will be continuously recorded while the mother/caregiver provides routine care. Annotations as described in the Data Collection Form will be documented by the research team regarding movements, breast-feeding attempts, cleaning/drying, patting, etc. (see Appendix 1). The vital signs data displayed on the monitors will only be visible to designated research team member(s), and all alarms will be turned off so as not to disturb parents and newborn. Any clinically relevant changes observed in vital sign parameters will be communicated by the research team member(s) to the obstetrical/neonatal team. A clinically relevant event is defined as follows: HR < 100 bpm or SpO₂ <85% (after the first 10 minutes of life) with sinusoidal wave as detected on either monitoring system during the course of the 2hr continuous monitoring. If the neonate requires any intervention to reverse instability, such as oxygen therapy and ventilator support, data collection will end but the data collected up to that time point will be included. The participating baby will not be withdrawn from the study.

The following data will be collected:

- Skin assessment:* In order to assess the safety of the wireless skin sensors, photographs of the infant's skin will be taken before device placement and after device removal. Each participating site will send de-identified digital photos coded (with the participant's study code) to the dermatologist for blinded assessment using the skin score (Neonatal Skin Condition Score - NSCS) as described in the Data Collection Form.
 - **Neonatal Skin Condition Score (NSCS)³⁷:** Photographs of the infant's skin at the site of device placement for both the chest and limb skin sensors will be taken prior to device

placement and following device removal. These photographs will then be scored by a dermatologist using the NSCS. Scores range from 3 (intact skin condition) to 9 (very poor skin condition).

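### The Bland-Altman analysis of continuous paired signals states neither its unit nor a within-infant variance component, so the agreement limits or their confidence intervals could be substantially too narrow

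*Combined protocol and SAP*

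**What the plan says.** Aim 3 (Section 2.2) is "To assess the accuracy of this wireless system in measuring HR, RR", SpO2 and skin temperature against the wired system, summarised by correlation, slope, VAF and bias. Section 4, under the statistical analytical approach, adds a Bland-Altman plot analysis of bias "between the mean differences and estimate an agreement interval". That is all the plan says about the agreement interval. It does not say whether one plotted point is an infant or a paired sample, names no repeated-measures or clustered method, plans no confidence interval for the limits, and sets no acceptable width.

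The data are repeated within infants. Section 3.3.4 states: "Data will be continuously recorded while the mother/caregiver provides routine care". Section 3.3.3 has both systems recording over the first 2 h, the second being applied at 10-20 min of age. Section 1.3 reports that the group aligned the two signals "to allow sample-to-sample comparison".

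The Section 4 table gives phase 1a averages ± SD: HR bias 0.04 ± 0.32 bpm and VAF 91.5 ± 6.5%; SpO2 bias 1.43 ± 1.4% and VAF 18.9 ± 20.8%. It also gives expected margins of error for these measures in the new study.

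**The concern.** A difference between two monitors has two variance components: how much the average difference varies from infant to infant, and how much the difference varies from moment to moment within an infant. A clinician who asks how far one wireless reading may lie from the wired one needs limits that contain both. An ordinary Bland-Altman analysis assumes one independent pair per subject and separates neither.

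Two simple ways of carrying out the plan go wrong in different places. With one mean per infant, the within-infant component is averaged away and the limits are too narrow for individual readings. With all samples pooled as independent, both components are in the limits, but the number of independent observations is overstated.

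This matters because the events the study counts are defined on readings crossing a threshold (Sections 2.2 and 3.3.4), not on 2 h averages. A small average bias says little about the error at a given moment.

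**Working it through.** **1. What unit does the planning use?** Inputs from Section 4: 600 infants; "Assuming a two-sided significance of 0.05, a study power of 0.9"; "accounting for the drop-out rate of 0.04 in all calculations". So n = 600 × 0.96 = 576.

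Margin = (1.960 + 1.282) × SD × √(2/576) = 0.191 × SD.

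| Measure | SD | Computed | Stated |
|---|---|---|---|
| HR VAF | 6.5 | 1.24 | 1.24% |
| HR bias | 0.32 | 0.061 | 0.06 bpm |
| SpO2 VAF | 20.8 | 3.97 | 3.97% |
| SpO2 bias | 1.4 | 0.267 | 0.26% |

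The margins reproduce (the last one to within rounding of the SD: 1.35 gives 0.258). The planning therefore treats the infant as the unit. A ± SD on a correlation or a VAF also implies that each was computed within a recording or infant and then averaged, so the bias column is most naturally the same kind of summary. Whether that SD runs over the 96 recordings or the 25 infants is not stated. No within-infant variance of the differences enters the planning.

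**2. Limits if one mean per infant is used.**
- HR: 1.96 × 0.32 = ±0.63 bpm.
- SpO2: 1.96 × 1.4 = ±2.74 points.

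**3. Limits for individual readings (illustration).** The within-infant SD of the difference is not in the documents. Assumption: it is about √(1 − VAF) × S, where S is the within-infant SD of the signal, also assumed. Limits = ±1.96 × √(SD_between² + SD_within²), with the tabulated bias SD as SD_between.

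HR, √(1 − 0.915) = 0.292:

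| S (bpm) | SD_within | Limits (bpm) | Ratio to ±0.63 |
|---|---|---|---|
| 5 | 1.46 | ±2.9 | 4.7 |
| 10 | 2.92 | ±5.8 | 9.2 |
| 15 | 4.37 | ±8.6 | 13.7 |

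SpO2, √(1 − 0.189) = 0.901:

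| S (points) | SD_within | Limits (points) | Ratio to ±2.74 |
|---|---|---|---|
| 1 | 0.90 | ±3.3 | 1.2 |
| 2 | 1.80 | ±4.5 | 1.6 |
| 3 | 2.70 | ±6.0 | 2.2 |
| 5 | 4.50 | ±9.2 | 3.4 |

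A ratio of 2 is reached at S of about 1.9 bpm for HR, but only at about 2.7 points for SpO2.

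In a simulation of 576 infants with 480 paired samples each, at S = 10 bpm and 3 points, the infant-mean limits contained about 17% of HR and 64% of SpO2 paired differences, not 95%.

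**4. If samples are pooled as independent.** In the same simulation pooled limits contained about 95% of the differences, so the limits themselves hold. The standard error of the bias is understated by √(1 + (m − 1) × ICC), with m pairs per infant, ICC = SD_between²/(SD_between² + SD_within²), and within-infant errors assumed exchangeable. At S = 10 bpm the HR ICC is 0.1024/8.602 = 0.012; at S = 3 points the SpO2 ICC is 1.96/9.26 = 0.21.

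| m | HR | SpO2 |
|---|---|---|
| 9 (the 15-minute log in Appendix 1) | 1.05 | 1.6 |
| 120 (one per minute) | 1.55 | 5.1 |
| 7,200 (1 Hz for 2 h) | 9.3 | 39 |

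The sampling rate is not stated, so m is assumed. The last row is generous, because both systems are on together for only about 100-110 of the 120 minutes.

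**The case against.** The strongest reply is that this is loose wording and not a wrong method. In the Section 4 sentence the mean differences belong to the bias; the agreement interval follows as a separate item with no unit attached. The group's sample-to-sample alignment suggests it may well use paired samples, and the limits would then be about right. A third route, limits computed within each recording and then summarised, would also keep the moment-to-moment error. Nor does the interval stand alone: correlation, slope and VAF are reported beside it, and Aim 2 counts events the wireless system missed.

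Much of this stands. A reader might infer that the plan fixes the limits on infant means; the documents do not say so. A reader might also infer that limits and confidence intervals will both be several-fold too narrow. The two faults belong to alternative readings, no confidence interval for the limits is planned at all, and with the infant as unit the interval for the mean bias is sound. Nor do the documents support the inference that poor SpO2 tracking would pass as near-perfect agreement: even infant-mean limits would be 1.43 ± 2.74, or about −1.3 to 4.2 points, and a VAF of 18.9% would show beside them.

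What does not fall away is the omission. Pooling leaves any interval estimate wrong unless clustering is handled. The within-recording route leaves out between-infant variance: for SpO2 at S = 3, 1.96 × 2.70 = ±5.3 against ±6.0. One specification settles all three routes.

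**Conclusion.** The point holds in conditional form. Section 4 plans an ordinary Bland-Altman analysis for clustered, continuous paired data and states neither the unit nor a within-infant component. The phase 1a table and the infant-level planning lean towards one mean per infant but do not settle it.

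If that route is taken, the limits would be about ±0.63 bpm and ±2.7 points and would understate disagreement of single readings: for HR by roughly 5 to 14 times, for SpO2 by roughly 1.2 to 3.4 times. If samples are pooled, only the confidence intervals suffer, from negligibly to many-fold.

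The size rests on assumed within-infant signal SDs and on the VAF approximation. It also rests on phase 1a figures from 25 NICU infants recorded 8 h a day with an earlier chest sensor; this study uses a redesigned chest sensor and the RAD7 limb sensor in stable newborns over 2 h. The direction of each error does not depend on these assumptions, but the fold-changes do. No phase 1a figures are given for respiratory rate or skin temperature, so their size cannot be illustrated. This should be corrected before analysis; it does not call the design or the data collection into question.

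**What to change.** In Section 4, replace the plain Bland-Altman analysis with a repeated-measures version, for each of the four signals:

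- State that the unit is the time-aligned paired sample, nested within infant, and give the sampling interval used.
- Fit a mixed model to the paired differences with a random infant effect, and report both variance components.
- Define limits of agreement as bias ± 1.96 × √(between-infant variance + within-infant variance).
- Take confidence intervals for the bias and for both limits from a bootstrap that resamples whole infants. This also allows for serial correlation within a recording.
- Keep the per-infant mean bias as a secondary summary, labelled as describing infant averages.

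The cost is one paragraph of the plan and a small amount of extra analysis. No new data or infants are needed. The price is that the reported limits will be wider, and so less favourable to the device, than limits on infant means.
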